GetWell Loop is a SaaS platform that allows physicians to monitor signs and symptoms, and communicate with patients during the postoperative recovery process. The platform enables doctors to identify patients at risk of decline in the follow up period. Patients are engaged through mobile and web-based surveys, reminders, and information personalized to the patient's specific condition or treatment plan. The company's platform also collects patients' feedbacks and monitors status against expected progress. Alerts are sent to physicians or providers about patients who are at risk of treatment failures, complications, or hospital readmissions. Physicians are informed if patients are trending toward an adverse outcome based on the patient's responses. Along with helping to prevent readmissions, GetWell Loop can also help institutions collect patient-reported outcomes (PROs) data, which can be used to evaluate and improve quality measures.

GetWell Loop and the Cleveland Clinic are interested in collaborating on a clinical pilot study to demonstrate that high patient engagement leads to enhanced pre-operative preparation potentially reducing length of stay (LOS), readmissions / reoperations, discharge disposition to home rather than another facility, reduced need for in-person follow up, increased patient (and provider) satisfaction, and increased satisfaction survey completion rates after elective primary hip and knee arthroplasty (THA and TKA). These improvements can translate on higher financial savings through the episode especially in light of the alternative payment models.

Specific Aims: GetWell Loop is currently used by orthopedic groups around the country, and is believed to improve peri-operative outcomes after THA and TKA and mitigate risk by: 1. Enhancing patient engagement with providers, 2. Allowing patients to play an integral role in patient-reported outcomes, 3. Generating and relaying actionable pre- and post-operative reporting directly to the clinical team, and 4.

Detecting impending post-operative complications early, enabling timely intervention and preventing avoidable complications and readmissions.

The specific aims of this proposal are to:

- 1. Measure the impact of using GetWell Loop on patient (and provider) satisfaction
- 2. Understand the degree to which high post-operative engagement reduces the need for in-person or telephone follow up appointment time

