 - a. Does the use of GetWell Loop lead to fewer potentially avoidable healthcare utilization encounters such as Emergency Department and hospital visits (including readmissions and reoperations)?
 - b. Does utilizing GetWell Loop improve clinical workflow by minimizing telephone calls and thereby offloading support staff, allowing them to be more efficient?
 - c. Does utilizing GetWell Loop reduce the volume of on call pages by addressing patient questions up front, alleviating concerns, and providing them with the information they need when they need it?
 - d. Does utilizing GetWell Loop allow the practice to identify patients whose inperson follow up needs are minimal, thereby freeing new referrals slots and enhancing same-day access?
 - e. Does GetWell Loop improve the throughput of patients by eliminating unnecessary follow-up appointments?
- 3. Measure length of stay, discharge disposition (home versus extended care facility) and 90 days readmission and reoperation rates
 - a. Does the early detection of adverse signs/symptoms that develop between clinical encounters result in earlier intervention that thereby reduces readmission and reoperations?
 - b. Do Patient Reported Outcomes (PROs), collected at intervals between clinical encounters, provide useful information which facilitates the detections of post-acute complications prior to the next clinical encounter?
 - c. Does patient adherence to instructions as well as recommended activity levels, captured through continuous activity monitoring such as the Jawbone Up Band (a wristband capable of measuring activity), predict time to recovery, functional outcomes, and potential failure rates? (optional)
- 4. Evaluate the financial impact of GetWell Loop in the episode of care

Methods: The study design is a prospective randomized trial in which patients undergoing selected hip and knee orthopedic procedures will be offered peri-operative use of GetWell Loop vs standard care. Approximately 300 patients will be enrolled (150 in each group).

Phase 1: 6 month run-in with 9 month follow (total of 12 month long study). Will collect the following outcome measures:

- Demographics (Age, gender, BMI)
- Comorbidities
- Surgery details (Length of surgery, laterality, surgeon)
- LOS and discharge disposition
- Number/length of follow up visits within 90 days (in person and telephone)
- 90 days readmission and reoperations
- Patient and provider satisfaction survey completion rates

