- Patient satisfaction (VAS scale and PPE-15)

Phase 2: 3 months for statistical analysis and writing manuscript.

Study Participants

- A. Patients Total Hip and Total Knee Arthroplasty patients treated at Avon Hospital
 - a. Inclusion criteria
 - i. Primary THA or TKA patient
 - ii. Personal consent to participate
 - iii. Have internet access or mobile access with a valid email address at the time of enrollment
 - iv. Above the age of 18 and are capable of consent
 - v. English speaking patient
 - b. Exclusion criteria
 - i. Staged arthroplasty procedure within 6 months of the index procedure
 - ii. Abandoned email address of record (e.g. bounce of email from clinic). If so, then data may be censored in the pilot analysis
 - iii. Less than 14 days until scheduled surgery

iv. Outpatient surgery

Data Analysis Plan

The difference in percent of respondents indicating a problem on the PPE-15 between treatment and control groups will be calculated as [percent of standard of care respondents reporting a problem, averaged across all PPE-15 domains] – [percent of GetWell Loop respondents reporting a problem, averaged across all PPE-15 domains], such that a positive difference indicates that the GetWell Loop group was more satisfied than the standard of care group, while a negative value indicates the opposite. A superiority hypothesis test using the two-independent sample t-test will be used to statistically evaluate the difference in the average satisfaction between groups. All other outcomes will be analyzed using chi-square tests for categorical variables and t-tests for continuous variables. Regression analysis will be conducted for multivariate analysis.

Schedule of Events

Evaluation	History	IntraOp	90 days postop	90 days	1 year
	/ PreOp		(Chart Review)	postop	(study completion)
				(survey)	
Demonstration	V				
Demographics	Λ				
Medical	X				
History/Comorbidities					
		V			
Surgical Details		X			
Discharge (LOS, disposition)			Х		
Track				Х	
Readmission/Reoperation					
Track ED visits, office visits				Х	
Track calls and on-call pages				Х	
Adverse Events			Х	Х	
Patient Satisfaction				Х	
VAS and PPF-15					
Provider Satisfaction Survey					Х

Study Metrics

Metric	Justification
Patient satisfaction VAS and PPE-15 (attached)	-Substantial opportunity for the Cleveland Clinic to differentiate itself among health systems and enhance revenue associated with patient satisfaction measures

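### No outcome is declared primary, no significance level or multiplicity rule is stated, and about 13 to 16 between-arm outcomes are to be tested without adjustment

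*Combined protocol and SAP*

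**What the plan says.** The Introduction and Background sets the purpose: to "demonstrate that high patient engagement leads to enhanced pre-operative preparation potentially reducing length of stay". The same sentence goes on to readmissions and reoperations, discharge home, need for in-person follow-up, satisfaction and survey completion. The Specific Aims add ED and hospital use, telephone calls, on-call pages and financial impact.

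The Phase 1 list in Methods puts two satisfaction instruments on one line, "Patient satisfaction (VAS scale and PPE-15", beside entries such as "LOS and discharge disposition" and "Patient and provider satisfaction survey completion rates". It does not rank them.

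The Data Analysis Plan defines a contrast for the PPE-15 only and says: "A superiority hypothesis test using the two-independent sample t-test will be used to statistically evaluate the difference in the average satisfaction between groups". The remaining outcomes follow in one sentence: "All other outcomes will be analyzed using chi-square tests for categorical variables and t-tests for continuous variables". It closes with "Regression analysis will be conducted for multivariate analysis", naming neither outcomes nor covariates.

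The document contains no primary or secondary label, significance level, sidedness, testing order, multiplicity adjustment or exploratory label. Methods gives about 300 patients, 150 per group, with no power calculation, so the sample size does not point to a deciding outcome either.

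**The concern.** A randomised trial that plans a superiority test should say beforehand which result decides whether superiority is shown. Here the reader must infer it. If PPE-15 showed no difference while VAS satisfaction, length of stay or ED visits reached significance, nothing in the plan says what would be concluded. Given a purpose that spans many outcomes, such a result could be reported as a demonstrated gain without departing from the plan. The unspecified regression allows a further adjusted result for any outcome. At stake is the false-positive rate of the claim that the platform improves outcomes, which the plan leaves uncontrolled.

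**Working it through.** The plan states no error rate, so there is no figure of its own to reproduce.

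**Step 1: count the between-arm outcomes.** Sources are the Phase 1 list, the Schedule of Events and Study Metrics. I merged hospitalisation with readmission, and office visits with in-person follow-up visits.

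- PPE-15: 1
- VAS satisfaction: 1
- Survey completion: 1 to 2 (patient, provider)
- Length of stay: 1
- Discharge disposition: 1
- Follow-up visits: 2 to 4 (number and length, in person and by telephone)
- Readmission: 1
- Reoperation: 1
- ED visits: 1
- Calls: 1
- On-call pages: 1
- 90-day cost: 1

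Minimum: 1+1+1+1+1+2+1+1+1+1+1+1 = 13. Maximum: 13 + 1 + 2 = 16. Potentially preventable events are left out because Study Metrics compares them with the previous year. Adverse events, provider satisfaction and the regression results are also left out. I start the calculation at k = 12 to allow for one further overlap, such as calls with telephone follow-up.

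**Step 2: level.** None is stated. I assume two-sided 0.05 per test, which is 0.025 in the direction favouring GetWell Loop.

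**Step 3: formulas, with no true effect on any outcome.**

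- Independent tests, either direction: 1 − 0.95^k. For k = 12, 1 − 0.95^12 = 46.0%; for k = 16, 1 − 0.95^16 = 56.0%.
- Independent tests, false benefit: 1 − 0.975^k. For k = 12, 26.2%; for k = 16, 33.3%.
- Common correlation ρ between normal test statistics, with c = 1.96, by numerical integration over a shared standard normal x. Either direction: 1 − ∫[Φ((c − √ρ·x)/√(1−ρ)) − Φ((−c − √ρ·x)/√(1−ρ))]^k φ(x)dx. False benefit: 1 − ∫[Φ((c − √ρ·x)/√(1−ρ))]^k φ(x)dx.

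**Step 4: results.** Each cell gives either direction / false benefit.

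| k | ρ = 0 | ρ = 0.3 | ρ = 0.5 | ρ = 0.7 |
|---|---|---|---|---|
| 12 | 46.0% / 26.2% | 39.7% / 20.2% | 31.9% / 16.0% | 23.2% / 11.6% |
| 14 | 51.2% / 29.8% | 43.8% / 22.4% | 34.8% / 17.4% | 24.9% / 12.4% |
| 16 | 56.0% / 33.3% | 47.6% / 24.4% | 37.4% / 18.7% | 26.4% / 13.2% |

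**Step 5: variants.** Counting only the 6 to 8 outcomes in the purpose sentence, independent tests give 1 − 0.95^6 = 26.5% to 1 − 0.95^8 = 33.7% in either direction, and 1 − 0.975^6 = 14.1% to 1 − 0.975^8 = 18.3% for false benefit. If every test were one-sided at 0.05, the independent false-benefit figure would be 46.0% (k = 12) to 56.0% (k = 16).

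**Step 6: after the fix.** With one primary outcome at two-sided 5%, the deciding claim has a 5% error rate, of which 2.5% is in the direction of benefit.

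**The case against.** The strongest reply is that the plan already singles out the PPE-15. It alone has a defined contrast, a direction of benefit and "A superiority hypothesis test using the two-independent sample t-test". The document title leads with patient satisfaction, and satisfaction is the first aim. The other outcomes are only to be analysed, and several aims are framed as measuring or evaluating. The study also calls itself a pilot, and the purpose sentence is hedged. Much of this stands. PPE-15 is the implied lead, the gap is a missing declaration rather than an undifferentiated list, and pilot status weakens the case for strict family-wise control over every outcome. It does not remove the need to declare the deciding outcome, because the same sentence speaks of demonstrating gains and a superiority test is planned.

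A reader might infer three stronger things that the documents do not support:

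- That all outcomes are tested at one common level. No level is given for any test; 5% is my assumption.
- That the plan counts any single significant outcome as success. It states no success criterion at all. The family-wise figures show the exposure if claims are made that way, not the error rate of a written rule.
- That the chance of a false benefit is one in three to one in two. That range roughly describes a false difference in either direction. It describes false benefit only under one-sided 5% tests, which the plan does not specify.

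Readmission, reoperation, ED visits and cost overlap, so correlations above 0.5 are possible for some pairs. The 0.7 column covers this.

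**Conclusion.** The point holds in a limited form. No outcome is labelled primary, no significance level or multiplicity rule is given, and about 13 to 16 between-arm outcomes go to unadjusted tests. For 12 to 16 outcomes and correlation from 0 to 0.5, the chance of at least one false significant difference is about 32%–56%. The chance of at least one falsely favouring GetWell Loop is about 16%–33%, roughly one in six to one in three. At correlation 0.7 the ranges are about 23%–26% and 12%–13%. Even 11.6%, the lowest false-benefit figure in the table, is more than four times the 2.5% that a single two-sided test allows (11.6/2.5 = 4.6).

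These figures rest on the assumed 5% level, my count of outcomes, equal correlation, and no true effect on any outcome. The absence of a declared primary outcome rests on none of these assumptions.

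**What to change.** In the Data Analysis Plan, name the PPE-15 average problem score as the sole primary outcome, tested at two-sided 5%, and the only basis for concluding superiority. Label every other outcome, VAS satisfaction included, as secondary or exploratory, reported as an estimate with a 95% interval and no confirmatory claim.

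If the sponsor wants confirmatory secondary claims, it should fix a short list in advance, define each item as a single measure, and test the list with Holm only after PPE-15 is significant. Without that gate, a 5% primary test and a separate 5% secondary family could together reach about 10% (0.05 + 0.05). With seven items, for example, the first Holm step would be 0.05/7 = 0.007. This secondary family is optional; the primary designation is the essential part.

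The change is to wording only and needs no extra patients or data. The downside is that a significant result on length of stay, readmission, ED visits or cost alone could no longer be presented as demonstrated benefit.

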Physician and staff satisfaction	- Opportunity to demonstrate clinical adoption rates and low barriers to implementation.
Total 90 day post-operative cost from index date+1 (same day) or from index date + LOS (inpatient)*	GetWell Loop templates should be able to either prevent the complication, or through early detection at the clinic level, reduce expense through minimized emergency room visits and readmissions.
*Claims submitted within 90 days must be limited to ICD-10s listed below (or to hospitalization due to ICD-10s below) in order to exclude unrelated claims.	
90 day post-op hospitalization rate (this is a readmission if initially an inpatient procedure, or an admission if initially an outpatient procedure)*	
*Must be associated with ICD-10s listed below in order to exclude unrelated readmissions.	
90-day ED Visit Rate* *Must be associated with ICD-10s listed below in order to exclude unrelated ED visits.	
Number of follow up visits within 90 days	Demonstration to physicians and practices the potential to improve throughput and workflow efficiency by minimizing the number of follow up visits required.
Potentially preventable readmissions	Potentially preventable admissions, events, ED visits. Using an approach similar to 3M's

Potentially Preventable Events grouping software, we will examine all events (ED visits, admissions, complications) for relation to index event, and compare this rate to prior year. Data may be
supplemented by Physician survey.
http://solutions.3m.com/wps/portal/3M/en_US/H ealth-Information-Systems/HIS/Products-and- Services/Products-List-A-Z/PPR-and-PPC-Grouping- Software/

ICD-10 codes for relevant metrics

Description		ICD-10
1.	Must be in 1 st or 2 nd diagnosis and must not be chronic, or	
2.	If patient is admitted, must be in 1 st or 2 nd diagnosis on hospital discharge.	
Infection and inflammatory reaction due to internal prosthetic device, implant, and graft		
•	Due to unspecified implant, device, and graft	T8579XA
•	Due to internal joint prosthesis	T8450XA
•	Due to other internal orthopedic device, implant and graft	T8460XA
Other	complications of internal prosthetic device, implant, and graft	
•	Due to unspecified implant, device, and graft	T859XXA
•	Due to internal joint prosthesis	T8481XA-
•	Due to other internal orthopedic device, implant, and graft	T8486XA; T8489XA; T849XXA
Postoperative infection		K6811
•	Other post-operative infection (abscess, septicemia)	T814XXA
Disrup	tion of wound	

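### The Schedule of Events assigns 90-day readmissions, visits, calls and pages to the survey, while Study Metrics needs coded records for hospitalization, ED visits and cost; neither is said to govern

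*Combined protocol and SAP*

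**What the plan says.** The Schedule of Events has two separate columns at 90 days, one for chart review and one for the survey. Three rows carry a single mark, in the survey column: "Readmission/Reoperation", "Track ED visits, office visits" and "Track calls and on-call pages". The patient satisfaction scales sit in the same column. Discharge data ("Discharge (LOS, disposition") are marked under chart review only. "Adverse Events" is marked under both.

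Study Metrics attaches an ICD-10 condition to three metrics: 90-day cost (through claims), 90-day hospitalization and 90-day ED visits. For ED visits it reads "Must be associated with ICD-10s listed below in order to exclude unrelated ED visits". The code table that follows requires the code in first or second diagnosis position, on hospital discharge if the patient is admitted. It also adds codes because ED coding is imprecise. Study Metrics further plans to examine every ED visit, admission and complication for its relation to the index event, possibly supplemented by a physician survey.

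The Phase 1 outcome list in Methods asks for "Number/length of follow up visits within 90 days (in person and telephone"). Aim 2c asks about the volume of on-call pages.

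The Introduction and Background lists among the expected benefits of GetWell Loop "increased satisfaction survey completion rates after elective primary hip and knee arthroplasty", and Phase 1 lists survey completion rates as an outcome. The Data Analysis Plan assigns chi-square and t-tests to all outcomes other than the PPE-15. It states no denominator and no handling of survey non-response for them.

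**The concern.** The schedule is the table that site staff work from. Followed literally, it sends them to a patient questionnaire for outcomes that two other parts of the protocol describe in terms of records. Two problems follow.

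First, a questionnaire does not yield a diagnosis code or its position, so the hospitalization, ED and cost metrics could not be derived from the scheduled source. Visit length and page counts are not tied to the ICD-10 rule, but practice records are a more natural source for them than patient recall at 90 days.

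Second, event capture would depend on response to the survey that carries the satisfaction scales. The protocol expects the intervention to increase completion of satisfaction surveys. Ascertainment could then differ between arms for a reason unrelated to the events themselves. Patients who are in hospital, have died or have done badly may also be less likely to answer.

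The utilization questions under Aim 2, readmission and reoperation under Aim 3, and part of the financial question in Aim 4 draw on these data.

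**Working it through.** The plan gives no figure to reproduce. Its only relevant number is about 300 patients, 150 per group, with no alpha, power, event rate or response rate behind it. The check therefore compares the sections and then illustrates the mechanism on assumed rates.

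**Step 1: scheduled source against required source.**

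| Outcome | Schedule of Events | Required elsewhere |
|---|---|---|
| Readmission (hospitalization) | survey only | listed ICD-10 code, first or second discharge diagnosis |
| Reoperation | survey only | 90-day rate; no ICD-10 condition of its own |
| ED visits | survey only | listed ICD-10 code |
| Office visits | survey only | number and length; no ICD-10 condition |
| Calls and pages | survey only | volume (Aims 2b, 2c); no ICD-10 condition |
| 90-day cost | no row | claims limited to listed codes |
| Length of stay, disposition | chart review only | consistent |
| Adverse events | chart review and survey | not defined further |

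The adverse-events row shows that the table can express two sources. It does not do so for the three rows at issue. The table was read from extracted text with some broken labels. The column positions are consistent across rows but should be confirmed against the original.

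**Step 2: what survey-only capture could do.** All rates here are assumptions. Let N = 150 per arm, true 90-day readmission p = 6% in both arms (150 × 0.06 = 9 events), response r = 80% with GetWell Loop and 65% with standard care, and event rate q in non-respondents. Respondents are assumed to report fully.

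Events captured = N·p − N·(1 − r)·q. The respondent rate is captured/(N·r), with N·r = 120 and 97.5.

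| q | Captured, GetWell Loop | Captured, standard care | Rate among respondents | Rate over all 150 |
|---|---|---|---|---|
| 12% | 9 − 3.6 = 5.4 | 9 − 6.3 = 2.7 | 4.5% vs 2.8% (+1.7 points) | 3.6% vs 1.8% (+1.8) |
| 6% | 9 − 1.8 = 7.2 | 9 − 3.15 = 5.85 | 6.0% vs 6.0% (0) | 4.8% vs 3.9% (+0.9) |
| 3% | 9 − 0.9 = 8.1 | 9 − 1.575 = 7.425 | 6.75% vs 7.6% (−0.9) | 5.4% vs 4.95% (+0.45) |

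There is no true difference in any row. Among respondents the sign depends on q. Over all randomised patients, with the survey still the only source, the arm that responds more appears worse in all three rows. Changing the denominator alone therefore does not cure the problem; the source has to change too.

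For scale, the standard error of the first respondent comparison is √(0.045 × 0.955/120 + 0.0277 × 0.9723/97.5) = 0.025, or 2.5 points. A 1.7-point artefact is below one standard error, but it is 1.7/6 = 28% of the assumed true rate and is systematic.

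**Step 3: a second set of assumptions.** Take a true rate of 10% in both arms. In standard care, response is 50% in patients with an event and 70% in those without; with GetWell Loop it is 80% and 90%. Observed rates are 0.05/(0.05 + 0.63) = 7.4% and 0.08/(0.08 + 0.81) = 9.0%, a spurious 1.6 points. If response is unrelated to the event within each arm (70% and 90% throughout), both arms show 10% and the respondent comparison is unbiased.

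**Step 4: precision.** If only respondents counted, response of 90% to 50% would leave 270 to 150 patients. Power for 15% vs 5% (assumed rates, two-sided alpha 0.05 assumed) would fall from 0.83 with all 300 to between 0.79 and 0.53.

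**The case against.** The best counter-argument is that the protocol plainly foresees coded records. Study Metrics speaks of claims, discharge diagnoses, ED coding and examination of all events, and the only survey it names is a physician survey, as a supplement. The schedule rows are worded as tracking. Because on-call pages are a practice-side workload measure, the survey column may simply mark the 90-day point at which tracking closes. Adverse events are already under chart review and may catch some readmissions and reoperations.

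Much of this stands. A reader might infer from the schedule that these outcomes will exist only for survey respondents and that the ICD-10 rule cannot be applied at all. The documents do not support that. No section limits these outcomes to respondents (the respondent wording concerns the PPE-15), and the ICD-10 rule is itself evidence that coded sources were intended. Nor does the rule cover the whole list: it is not stated for office visits, calls, pages or reoperations as such. The illustrated bias rests wholly on assumed rates and arises only if the survey really is the source.

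What the objection does not remove is the conflict. If charts and claims were always intended, the schedule is wrong and staff following it would collect the wrong data. If the survey was intended, the coded metrics cannot be derived from it. Either way the text needs correcting.

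**Conclusion.** The point holds as an unreconciled conflict over data source. The schedule assigns readmission/reoperation, ED and office visits, and calls and pages to the 90-day survey alone. Study Metrics needs coded claims or discharge diagnoses for hospitalization, ED visits and cost, and no section says which source takes precedence.

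Loss of data is not established; it would follow only if the schedule were applied as written. Capture would then depend on a response rate that the protocol expects to differ by arm. The size and direction of any bias are unknown. The illustrations give spurious respondent differences from −0.9 to +1.7 points, and none when response is unrelated to the event within arm. They show a mechanism and are not estimates.

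Length of stay, discharge disposition and the PPE-15 comparison are not touched by this point. The conclusion assumes that the column placement in the original table matches the extracted text. The plan should be corrected because the remedy is cheap and several secondary aims use these data.

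**What to change.** 1. In the Schedule of Events, mark readmission/reoperation, ED and office visits, and calls and on-call pages under the 90-day chart-review column for every randomised patient.
2. State the primary source for each outcome: coded chart or claims records for readmission, reoperation, ED and office visits; practice telephone and paging records for calls and pages. Apply the ICD-10 condition only to the metrics that already carry it.
3. Keep the survey mark as a supplement for events outside the health system, and say how a survey-only report with no code is classified.
4. State in the Data Analysis Plan that these outcomes use all randomised patients, not survey respondents, as the denominator.

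A chart review is already planned at 90 days, so the cost is a table edit, a few sentences and some extra abstraction time. Telephone and paging records may need a separate extract. Out-of-system events will still depend partly on the survey, so some differential capture can remain; reporting survey response by arm would let readers judge it.

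### The potentially preventable readmissions metric is compared only with an undefined prior year, and nothing names the randomised standard-care arm as its comparator

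*Combined protocol and SAP*

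**What the plan says.** The Methods section describes a prospective randomised trial in which "patients undergoing selected hip and knee orthopedic procedures will be offered peri-operative use of GetWell Loop vs standard care", with this size: "Approximately 300 patients will be enrolled (150 in each group"). Aim 2a asks: "Does the use of GetWell Loop lead to fewer potentially avoidable healthcare utilization encounters such as Emergency Department and hospital visits".

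In the Study Metrics table, the Justification column for potentially preventable readmissions goes beyond rationale and gives an instruction: "we will examine all events (ED visits, admissions, complications) for relation to index event, and compare this rate to prior year". The phrase occurs nowhere else in the document. The period, site, patients, number and data source of the prior-year cohort are not given. Nor is it said whether the trial's rate comes from the GetWell Loop arm or from all trial patients.

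The Data Analysis Plan names the two arms only for satisfaction: "The difference in percent of respondents indicating a problem on the PPE-15 between treatment and control groups will be calculated as" standard of care minus GetWell Loop. For everything else it says: "All other outcomes will be analyzed using chi-square tests for categorical variables and t-tests for continuous variables". That sentence names tests but no groups.

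**The concern.** Randomisation supplies a concurrent control, but the one comparator written for this metric is a historical one. Three things could separate a prior-year cohort from the trial patients even if the product did nothing:

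- **Calendar time.** Practice, case mix or coding may change between the two periods.
- **Selection.** Trial patients must meet the criterion "Personal consent to participate", which cannot be applied to a prior-year cohort.
- **Ascertainment.** The Schedule of Events tracks ED visits, readmissions, reoperations and adverse events at 90 days, and the row allows a physician survey to supplement the data. Nothing says that prior-year events would be found in the same way.

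The bias could run in either direction. This is the row that sorts events into potentially preventable or not, which is the language of aim 2a. If the row is followed as written, a difference could appear, or a real one be hidden, for reasons unrelated to GetWell Loop, and the randomised comparison would not be the stated result for this metric.

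**Working it through.** **Text check.** Three places bear on the comparator for this metric.

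| Place | What it settles |
|---|---|
| Methods | Two randomised arms exist, about 150 each |
| Data Analysis Plan, sentence on other outcomes | Type of test; no groups named |
| Study Metrics, this row | Comparator is the prior year, undefined |

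The general sentence follows two sentences about a between-group satisfaction comparison, so it can be read as covering this metric between arms. But a chi-square test can equally be run against a historical cohort, and the sentence does not withdraw the row's specific instruction. The Phase 1 outcome list does not help: it has 90-day readmission and reoperation, not the potentially preventable classification.

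**Illustration of size.** The plan has no figure to reproduce: it states no event rate, drift, prior-year size or alpha. All of these are assumed below. Only the 150 and 300 trial patients come from the plan.

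Let p0 and N be the prior-year rate and size, and p1 and n the trial rate and size. There is no product effect, and the test is a two-sided 5% pooled two-proportion test (equivalent to the chi-square test), so 2.5% is nominal in each direction. The probability of a significant result in the direction of the drift is

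P = Φ( [ |p0 − p1| − 1.96·√(p̄(1 − p̄)(1/N + 1/n)) ] / √(p0(1 − p0)/N + p1(1 − p1)/n) ), with p̄ = (N·p0 + n·p1)/(N + n).

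Worked case: p0 = 0.08, p1 = 0.06, N = 300, n = 150.

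- p̄ = (24 + 9)/450 = 0.0733
- Standard error under the null = √(0.0733 × 0.9267 × (1/300 + 1/150)) = 0.0261
- Standard error under the drift = √(0.08 × 0.92/300 + 0.06 × 0.94/150) = 0.0249
- P = Φ((0.02 − 1.96 × 0.0261)/0.0249) = Φ(−1.25) = 0.106

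All cases with p0 = 0.08:

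| Trial rate | False result | N=300, n=150 | N=600, n=150 | N=300, n=300 | N=600, n=300 |
|---|---|---|---|---|---|
| 6% | benefit | 10.6% | 11.0% | 15.8% | 18.0% |
| 10% | harm | 11.3% | 13.5% | 13.5% | 17.8% |
| 7.2% | benefit | 4.6% | 4.6% | 5.6% | 5.9% |
| 8.8% | harm | 5.0% | 5.5% | 5.4% | 6.3% |

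The n = 300 columns apply only if both arms are pooled against the prior year, which the row does not rule out. Exact binomial enumeration of the 6% row gives 10.2%, 10.6%, 16.1% and 18.0% in the same column order.

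If both randomised arms share one rate, the between-arm test stays at about 2.5% in each direction whatever the calendar drift.

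**Precision given up.** The 95% half-width is 1.96·√(p0(1 − p0)/N + p1(1 − p1)/n).

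- Between arms, 6% in each, 150 against 150: 1.96·√(2 × 0.06 × 0.94/150) = 5.4 points
- 8% in 300 prior-year patients against 6% in 150: 4.9 points
- 8% in 600 prior-year patients against 6% in 150: 4.4 points

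Between-arm power for a halving from 8% to 4% with 150 per arm, by the first formula: Φ((0.04 − 1.96 × 0.02742)/0.02733) = Φ(−0.50) = 30.7% (exact 30.0%).

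**The case against.** The strongest reply is that the document already answers the question. In a two-arm randomised trial, a sentence about all other outcomes that directly follows a between-group test naturally means between arms. The prior-year remark sits in a justification column and could be an added benchmark. That reading is plausible, and the text does not prove that the randomised comparison would be omitted. It does not settle the matter, because the row is the more specific instruction and names a different comparator.

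The second reply is about scope. The 90-day hospitalisation and ED visit metrics are limited to listed ICD-10 codes and carry no prior-year wording, nor does readmission/reoperation. Aim 2a therefore keeps endpoints with no historical comparator. This stands: only the potentially preventable classification is exposed, and it is not in the Phase 1 list.

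Third, every rate is assumed, and the row says only that the rates will be compared. If that comparison is descriptive, no false-positive rate applies. The larger figures need a 25% relative shift, and the largest also need the arms pooled, which would not test the product. This also stands: the figures show the kind of risk, not its actual size.

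Finally, the repair needs more than a comparator. It brings in an analysis population that the plan does not state, which touches the exclusion criterion allowing data to be censored for abandoned email addresses. It also needs a relatedness rule, which the row describes only as similar to commercial grouping software. Both points are fair and belong in the cost.

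**Conclusion.** The concern holds. For this one metric the plan writes down a non-randomised, undefined comparator and nowhere names the standard-care arm. The general analysis sentence makes the intention uncertain without correcting it. Under the assumed 8% prior-year rate and no product effect, a two-point drift raises the one-directional false-positive rate from 2.5% to about 11% to 13.5% with the 150 GetWell Loop patients, and to as much as 18% if both arms are pooled. A 10% relative drift raises it to about 4.6% to 6.3%. These figures depend on the assumed rates, cohort sizes and a significance test being applied; the conclusion about the text does not. The change should be made, but it is limited to this row and leaves the other 90-day utilisation metrics as they are.

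**What to change.** In the Study Metrics row, replace the instruction "and compare this rate to prior year" with wording such as: compare this rate between the GetWell Loop and standard-care arms among all randomised patients, with relatedness to the index event classified by the same rule in both arms; any prior-year rate is descriptive context only.

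This needs one sentence and no new data collection, since the events are already tracked at 90 days. The sponsor should make sure that the abandoned-email provision is consistent with the stated population, and should write down the relatedness rule, including whether the physician survey applies to both arms. The price is a somewhat wider interval (about ±5.4 points, against ±4.4 to ±4.9 with the assumed historical cohorts). Power is low, at about 31% for a halving from 8% to 4%, so the result should be reported as an estimate with its interval and read cautiously.
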